## Statistical Analysis Plan

Functional improvement endpoints evaluated at baseline, 30 days, discharge, 12 months, and 2, 3, 4, 5 years are:

- New York Heart Association (NYHA) functional class improvement
- Quality of Life (QOL) assessed using the Kansas City Cardiomyopathy Questionnaire (KCCQ)
- 6 minute walk distance (6MWD)

The KCCQ and 6MWD are not required to be collected at discharge and will not be reported at discharge.

Echocardiographic endpoints evaluated at baseline, discharge, 30 days, 1 month, 12 months and 5 years are:

- MR Severity Grade
- Effective Regurgitant Orifice Area (EROA) as measured by measured by PISA method
- Coaptation Measures (depth/length) (Baseline only)
  - *Coaptation depth: Coaptation depth is defined as the distance from the plane of the mitral valve annulus to the first point of leaflet coaptation in the atrial-to-ventricular direction in the four-chamber view.*
  - *Coaptation length: Coaptation length is defined as the vertical length of leaflets that is in contact, or is available for contact, during systole in the atrial-to-ventricular direction in the four-chamber view.*
- Flail Measures (gap/width) (Baseline only)
  - *Flail Gap: Measured as the greatest distance between the ventricular side of the flail segment to the atrial side of the opposing leaflet. This distance is measured perpendicular to the plane of the annulus in two views and the largest measurement is used. The two views for measurement are the four-chamber long axis (LAX) view and the left ventricular outflow tract (LVOT) view.*
  - *Flail Width: Measured as the width of the leaflet segment that moves in and out of plane during systole in the short axis (SAX) view.*
- Grasping Area Anatomy (measure cleft or scallop if significant) (Baseline only)
- Assess chordal support (Baseline only)
- Regurgitant Jet(s) Position and Quantity (Baseline only)
- TR Severity: None, Mild, Moderate or Severe

The following study endpoints will be evaluated during the clinical trial for all MitraClip G4 PMCF Study subjects:

- Acute Procedural Success (APS) as defined above
- Major Adverse Events (MAE): defined as a composite of All-cause Death, Myocardial Infarction, Stroke, or non-elective CV surgery for device related complications
- MR Severity (evaluated at discharge, 30 days, 1 year and 5 years)
- Device Related Adverse Events (including mitral valve stenosis, device embolization, single leaflet device attachment (SLDA), myocardial perforation, or the need for mitral valve replacement instead of repair due at least in part to the MitraClip procedure or the presence of the MitraClip device)

*This confidential document is the property of Abbott and shall not be reproduced, distributed, disclosed or used without the express written consent of Abbott.*

## Statistical Analysis Plan

- All-cause mortality
- Recurrent heart failure hospitalization
- Quality of Life (QOL) assessed using the Kansas City Cardiomyopathy Questionnaire (KCCQ)
- New York Heart Association (NYHA) functional class improvement
- 6 minute walk distance (6MWD) (per standard of care)

## 2.0 ANALYSIS CONSIDERATIONS

### 2.1 Analysis Populations

#### 2.1.1 Primary Analysis Population

A patient is considered enrolled upon signing and dating an informed consent form for participation. The primary analysis population will be defined as all enrolled subjects with a MitraClip G4 system implant procedure attempted.

#### 2.1.2 MitraClip G4 PMCF Study Population

The MitraClip G4 PMCF population will be defined as enrolled subjects with a MitraClip G4 system implant procedure attempted and are in the first 420 subjects enrolled in Europe.

## 2.2 Statistical Methods

Descriptive analysis will be performed to summarize baseline, clinical and safety event data. Depending on the type of data (e.g., continuous or categorical), statistical methods described in the following sections will be used. Only subjects in the primary analysis population, as defined in Section 2.1.1., will be included in this analysis.

#### 2.2.1 Descriptive Statistics for Continuous Variables

For continuous variables (e.g., age, etc.), results will be summarized with the numbers of observations, means, and standard deviations, with quartiles, minimums, maximums, and 95% confidence intervals for the means. Differences between subgroups, where specified, will be summarized with relative risks, the differences of the two means, and 95% confidence intervals for the difference between the means.

#### 2.2.2 Descriptive Statistics for Categorical Variables

For categorical variables (e.g. APS, etc.), results will be summarized with subject counts and percentages/rates, and where applicable, with exact 95% Clopper-Pearson confidence intervals, and p-values may be presented for hypothesis generating purposes. Differences between the two groups, when specified, will be summarized with the difference in percent and the Newcombe score 95% confidence interval for the difference of two percentages.

#### 2.2.3 Survival Analyses

Survival analysis will be conducted to analyze time-to-event variables, such as all-cause of mortality. Subjects without events will be censored at their last known event-free time point. Survival curves will be constructed using Kaplan-Meier estimates. Summary tables for endpoints will include event (failure)

This confidential document is the property of Abbott and shall not be reproduced, distributed, disclosed or used without the express written consent of Abbott.

## Statistical Analysis Plan

rates, Greenwood standard error and confidence interval for the event rates.

### 2.3 Primary Endpoint Analysis

For the EXPAND G4 Post Market study Phase II, there will be no hypothesis testing performed. This is a study with descriptive endpoint data in order to collect real world clinical experience of the MitraClip G4 System.

In the MitraClip G4 PMCF study, acute procedural success (APS) will be the only endpoint on which hypothesis testing will be performed. APS is defined as successful implantation of the MitraClip G4 Implant with resulting MR severity of 2+ or less on discharge Echocardiogram (30-day echocardiogram will be used if discharge information is unavailable or uninterpretable). Subjects who die or undergo mitral valve surgery before discharge are considered as an APS failure. This endpoint will be assessed as a proportion of subjects meeting the definition of APS and tested against a performance goal (PG) of 82.8%.

The null and alternative hypotheses are stated as:

$$H_0: \text{APS rate} \leq \text{PG}$$

$$H_A: \text{APS rate} > \text{PG}$$

  

The null hypothesis will be rejected (i.e., successfully passing the PG) if the p-value is calculated to be less than 0.05. The analysis will be performed on the MitraClip G4 PMCF population defined above.

### 2.4 Sample Size Calculations

No sample size calculations were performed for the EXPAND G4 Post Market Phase II study.

However, the sample size for the MitraClip G4 PMCF study were derived using APS. The expected APS rate for MitraClip G4 is assumed to be 88%. For a performance goal of 82.8%, an effective sample size of 400 subjects will provide 90% power using the exact test to reject the null hypothesis in Section 2.3 at

*This confidential document is the property of Abbott and shall not be reproduced, distributed, disclosed or used without the express written consent of Abbott.*

## Statistical Analysis Plan

a one-sided 5% significance level. Assuming a 5% attrition rate account for missing echocardiographic assessment or non-evaluable MR assessment at discharge, a sample size of 420 subjects is determined based on the primary endpoint of APS.

A meta-analysis with weights of inverse-variance method is used to analyze the APS in these MitraClip studies. The estimated APS rate from the meta-analysis is 87.8%, with 95% confidence interval of [82.8%, 92.7%]. Hence, the PG of the APS is set as the lower limit of 95% CI for APS from the meta-analysis, i.e. 82.8%. As MitraClip G4 system is expected to perform as good as or better than the first and secondary generation of MitraClip system, thus the expected APS of MitraClip G4 is assumed to be 88%.

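### With 420 enrolled and 5% non-evaluable, the PMCF test has about 89% power rather than 90%, and the documents disagree on whether 420 counts enrolled or evaluable subjects

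*SAP*

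**What the plan says.** The PMCF sub-study carries the only hypothesis test in the programme (SAP 2.3). Acute procedural success (APS) is "tested against a performance goal (PG) of 82.8"%, with rejection when p is below 0.05.

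SAP 2.4 supplies the design values:
- True rate: "The expected APS rate for MitraClip G4 is assumed to be 88"%.
- Power: "an effective sample size of 400 subjects will provide 90% power using the exact test", at "a one-sided 5% significance level".
- Loss: "Assuming a 5% attrition rate account for missing echocardiographic assessment or non-evaluable MR assessment at discharge".
- Result: "a sample size of 420 subjects is determined based on the primary endpoint of APS". The inflation formula is not given.

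Three places bear on what the 420 counts:
- SAP 2.1.2 limits the PMCF population to subjects with an attempted procedure who "are in the first 420 subjects enrolled in Europe".
- SAP 1.3 times the PMCF analysis to the point at which 420 European subjects have 30-day follow-up and the data needed.
- Protocol 3.2 takes the first European subjects whose APS data are evaluable (the number is redacted).

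Under SAP 2.8, a 30-day echocardiogram replaces a missing or unreadable discharge one, and any data still missing are excluded. Death or mitral valve surgery before discharge counts as an APS failure.

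**The concern.** The step from 400 to 420 adds 5% of the evaluable number, whereas the allowance is for losing 5% of those enrolled. Taking 5% off 420 leaves 399, one short of the effective size to which the 90% is attached. Because the SAP specifies an exact binomial test, one subject can matter: power does not rise smoothly with n, and 400 may be an unusually favourable value.

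This test decides whether the PMCF study succeeds (protocol Appendix II, section 9.6), and the PMCF study serves a CE-mark requirement. Its power statement should therefore describe what the planned enrolment delivers. At stake is the accuracy of that statement. Type I error, the performance goal and the success rule are unaffected.

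**Working it through.** **Inputs.** Null rate p0 = 0.828 (SAP 2.3); true rate p1 = 0.88, one-sided alpha 0.05, 400 effective subjects, 5% attrition and 420 planned (all SAP 2.4).

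**Method.** For each n, find the smallest count c with P(X ≥ c | n, 0.828) < 0.05. Power is P(X ≥ c | n, 0.88).

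**Step 1: reproduce the stated power.** At n = 400, c = 344, attained alpha is 0.0488 and power is 90.25%. The stated 90% is confirmed for 400 effective subjects.

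**Step 2: the inflation.**
- 400 × 1.05 = 420 exactly, the planned figure.
- 400 / 0.95 = 421.05, rounded up to 422.
- 420 × 0.95 = 399 expected evaluable; 422 × 0.95 = 400.9.

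**Step 3: power around the target.**

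| n evaluable | c | attained alpha | power |
|---|---|---|---|
| 399 | 344 | 0.0380 | 87.85% |
| 400 | 344 | 0.0488 | 90.25% |
| 401 | 345 | 0.0467 | 89.9% |
| 405 | 349 | 0.0388 | 88.5% |
| 406 | 349 | 0.0497 | 90.8% |
| 412 | 355 | 0.0378 | 88.8% |
| 419 | 360 | 0.0492 | 91.5% |
| 420 | 361 | 0.0470 | 91.2% |
| 424 | 365 | 0.0393 | 89.9% |

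The first n to reach 90% is 400. The next five (401 to 405) fall below it, and power stays at or above 90% only from n = 425. Over n = 395 to 424 it runs from 87.9% to 91.5%.

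**Step 4: average over random attrition.** The realised evaluable number is not fixed, so weight the exact power at each m by Binomial(N, 0.95):

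| N enrolled | mean power | chance that the realised n has power below 90% |
|---|---|---|
| 420 | 89.0% | 86% |
| 422 | 89.2% | 80% |

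With 420 enrolled, the chance of fewer than 400 evaluable is 53%.

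**Step 5: split the gap.** Correct inflation recovers 89.2 − 89.0 = 0.2 points. The remaining 90 − 89.2 = 0.8 points come from the exact test's discreteness. The 2.4-point fall between n = 400 and n = 399 (90.25 − 87.85) has the same origin: the cut-off stays at 344 while attained alpha drops from 0.0488 to 0.0380. By normal approximation the two powers are 90.2% and 90.1%.

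**Step 6: the other reading of 420.** If 420 are evaluable, c = 361 and power is 91.2%.

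**The case against.** The strongest reply is that nothing stated is wrong. SAP 2.4 ties the 90% to 400 effective subjects, where it reproduces, and never claims it for 399. The shortfall is at most two subjects in 420 (0.5%), and multiplication by 1.05 is inferred because no formula is printed. This largely stands. The inference is fair, since no rounding of 421.05 gives 420, but the slip is small.

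Second, 420 may not mean enrolled. SAP 1.3 and protocol 3.2 can be read as 420 with usable data, and protocol Appendix II speaks throughout of a minimum number. This stands as an unresolved conflict. It does not clear the plan: SAP 2.1.2 defines the population on which SAP 2.3 runs the test, and if 420 were evaluable the attrition step in SAP 2.4 would be redundant.

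Third, actual exclusions may be below 5%. The allowance refers to discharge assessments, the 30-day echocardiogram can stand in for those, and early deaths and surgery stay in the denominator as failures. The SAP does not say whether 5% is before or after substitution. Assuming a net loss of 3%, mean power from 420 enrolled is 89.7%; at 1% it is 90.1%. That narrows the gap, but 5% is the SAP's own planning figure.

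A reader might infer that the inflation error cuts power from 90% to 87.9%, or that the PMCF test is materially underpowered. The documents support neither. The first attributes a feature of the exact test to an arithmetic slip worth 0.2 points; the second does not fit an average of 89.0%.

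**Conclusion.** Minor, but real. On the SAP's assumptions (true APS 88%, goal 82.8%, one-sided exact 5% test, 5% non-evaluable independently at random) and the SAP 2.1.2 reading of 420 as enrolled with an attempted procedure, power is about 89% on average and 87.9% at the expected 399 evaluable subjects. The stated 90% is right for 400 evaluable subjects but does not carry over to 420 enrolled with 5% loss. About 0.2 of the one-point gap is the inflation slip; the rest is discreteness. If 420 means evaluable, power is 91.2% and there is no shortfall, so the main open question is one of definition.

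**What to change.** Amend the SAP wording as follows:

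1. In SAP 2.4, keep 90% for 400 evaluable subjects and add that 420 enrolled with 5% non-evaluable gives about 89% power on average (87.9% at exactly 399).
2. State that exact-test power runs from about 88% to 91% for n = 395 to 424, and stays at or above 90% only from 425 evaluable.
3. Reconcile SAP 2.1.2 with SAP 1.3 and protocol 3.2 on whether 420 counts enrolled or evaluable subjects. If evaluable, state 91.2% and delete the attrition step. If enrolled, say whether the 5% applies before or after the 30-day echocardiogram is substituted.

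If the sponsor prefers to correct the inflation to 422, the SAP may say that this targets 400 evaluable subjects, but not that it secures 90%: average power is 89.2%.

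The cost is a few sentences, with no change to the test or the goal and no extra subjects unless 422 is chosen. On the enrolled reading, the stated power becomes about one point less favourable.

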### 2.5 Interim Analysis

No formal interim analyses are planned for this study. Interim study reports with descriptive analysis may be produced for regulatory or reimbursement purposes.

### 2.6 Timing of Analysis

For the MitraClip G4 PMCF study, the analysis of the primary endpoint will be performed when the last subject completes the 30 days visit.

For the remaining endpoints in both the EXPAND G4 Post Market Study and MitraClip G4 PMCF study, the analysis will be performed after all subjects in the PMCF populations have completed 5-year follow-up visit, are discontinued from the trial or have passed the end of their 5-year visit window.

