#### 1.3 Clinical Investigation Design

This is a post-market, multi-center, single-arm, prospective study to assess the safety and performance of the next generation MitraClip G4 System in a contemporary, real-world setting. The current protocol describes two phases for targeting treatment of 1100 subjects at up to [REDACTED] sites in the Europe, the United States (US), Canada and Japan.

- *Phase I:* Included up to 100 patients at up to [REDACTED] sites in the US treated with a MitraClip G4 device and followed through 30 days (completed August 2020).
- *Phase II:* Includes 1,000 post-market, consented patients at up to [REDACTED] sites treated with a MitraClip G4 device according to local guidelines and IFU from the Europe, the United States, Canada and Japan followed through 5 years.

Follow-up echocardiograms for patients in Phase II will be collected at Discharge, 30 days and 1 year and 5 year at post-procedure visits. Additional clinical follow-up visits will be at 6 months (phone call), 2, 3, 4 year (office visits). Cardiovascular adverse events will be reported through 5 years to confirm safety of the MitraClip G4 System.

Additionally, the MitraClip G4 PMCF Study is a sub-analysis of the EXPAND G4 Post Market Study and will be conducted when 420 European subjects have completed 30-day follow-up with necessary data. An overall sample size of 1100 subjects will ensure at least 420 European subjects are treated with the MitraClip G4 System. Data from the MitraClip G4 PMCF Study will be used to fulfill the regulatory requirement for PMCF associated with the CE mark approval of the MitraClip G4 System.

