#### 1.4 Study Endpoints

The following study endpoints will be evaluated during the clinical trial for all Phase II subjects:

Safety: The assessment of safety will include all occurrences through 30 days post procedure.

- Occurrence of Major Adverse Events (MAE) at 30 days. MAE is defined as a composite of all-cause Death, Myocardial Infarction, Stroke, or non-elective Cardiovascular (CV) surgery for device related complications.

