### 2.8 Handling of Missing Data

If Echocardiography assessed MR severity at discharge is unavailable or cannot be assessed, the 30-day value will be used to assess APS. All analyses will be based on available data with missing data excluded. Any unused or spurious data will be noted as appropriate.

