## 3.0 DESCRIPTIVE ENDPOINTS AND ADDITIONAL DATA

### 3.1 Endpoints

For the EXPAND G4 Post Market Phase II study, the study endpoints as listed in section 1.4 will be evaluated descriptively in the primary analysis population. For the MitraClip G4 PMCF study, all study endpoints will be evaluated descriptively in the PMCF population.

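### The SAP releases the EXPAND G4 5-year analysis when the first 420 European subjects are complete, without waiting for the rest of the 1,000 Phase II subjects

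*SAP*

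**What the plan says.** SAP 2.6 first times the PMCF primary endpoint at the last subject's 30-day visit. Its second sentence has this scope: "For the remaining endpoints in both the EXPAND G4 Post Market Study and MitraClip G4 PMCF study". The condition set for all of these is that "the analysis will be performed after all subjects in the PMCF populations have completed 5-year follow-up visit", with discontinuation or passing the end of the 5-year window as alternatives to completion.

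The populations are defined elsewhere in the SAP:

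- Section 2.1.2: PMCF subjects had a procedure attempted and "are in the first 420 subjects enrolled in Europe".
- Section 2.1.1: the primary analysis population is every enrolled subject with an attempted procedure, without limit by region or number.
- Section 1.3: Phase II "Includes 1,000 post-market, consented patients", from Europe, the US, Canada and Japan, followed for 5 years. The overall size of 1,100 "will ensure at least 420 European subjects are treated with the MitraClip G4 System".
- Section 1.4, introducing the EXPAND G4 endpoints: "The following study endpoints will be evaluated during the clinical trial for all Phase II subjects".
- Section 3.1, for Phase II: "the study endpoints as listed in section 1.4 will be evaluated descriptively in the primary analysis population".

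On incomplete data, SAP 2.8 says: "All analyses will be based on available data with missing data excluded". SAP 2.2.3 censors event-free subjects at their last known event-free time.

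The visible text of CIP section 8 sets no analysis time for EXPAND G4. CIP Appendix II, section 9.4.3, concerns only the PMCF analysis at 30 days. SAP 2.6 is therefore the only visible rule for the EXPAND G4 5-year analysis.

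**The concern.** One study's analysis is released by the completion of a subset of its subjects. The rule sets an earliest time, and nothing in it makes that time depend on Phase II subjects in the US, Canada or Japan, or on European subjects after the 420th.

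If the rule is followed as written and accrual continues past the 420th European subject, some Phase II subjects will have no 5-year visit when the analysis is run. Under the available-data rule they drop out of the visit-based 5-year summaries: MR grade, NYHA class, KCCQ and 6MWD. Time-to-event endpoints keep them, but with extra administrative censoring close to 5 years. The 5-year results would then be less precise and would not cover the population named in SAP 1.4 and 3.1. The missing subjects would not be a random sample, since they would be the last to enrol.

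**Working it through.** **The plan's own figure: where 420 comes from.** SAP 2.4 uses an exact one-sided 5% test of 88% against a performance goal of 82.8%, with 400 evaluable subjects and 90% power. At n = 400 the smallest rejection count is 344, with exact alpha 0.0488 and power 0.902, so the stated power is reproduced. For 5% attrition, 400 × 1.05 = 420 (400/0.95 rounds up to 422). The 420 was therefore sized for a discharge endpoint, not as a marker of 5-year completeness in Phase II.

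**Subjects outside the trigger.** 1,000 − 420 = 580, or 58% of Phase II. This is an upper bound on the number affected. Only subjects still short of their 5-year visit when the analysis is run matter.

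**Subjects enrolled after the 420th European.** The documents give no accrual by region, so the following are assumptions. Phase I was US-only, so all Europeans are in Phase II, and 420 of 1,000 is a share of 42%. Let *s* be the European share of Phase II.

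- Assumption A, uniform accrual with all regions in parallel: 1000 × (1 − 0.42/*s*).
- Assumption B, Europe starting at fraction *r* of accrual (CIP 1.0 gives the CE Mark as the last approval): (1000*s* − 420) + 1000(1 − *s*)(1 − *r*)(1 − 0.42/*s*).
- Europeans beyond the 420th, whenever Europe starts: 1000*s* − 420.

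| European share | A | B, r = 0.25 | B, r = 0.5 | Europeans beyond 420th |
|---|---|---|---|---|
| 42% | 0 | 0 | 0 | 0 |
| 50% | 160 | 140 | 120 | 80 |
| 60% | 300 | 270 | 240 | 180 |
| 70% | 400 | 370 | 340 | 280 |

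A simulation of A with each subject European at random gave about 160, 300 and 400 at the three higher shares, and about 13 to 14 at 42%.

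**Allowance for the visit window.** CIP 6.4 allows −30/+90 days at 5 years. Let *d* be the day of the last PMCF visit relative to exactly 5 years, and let every later subject attend as early as allowed. The number recovered is then the accrual rate × (*d* + 30). Over 24 months (about 730 days) this is 1000/730 × 30 = 41 for *d* = 0, and 1000/730 × 120 = 164 for *d* = 90. Over 18 months it is 55 and 219. Subtracting from A, with a floor of 0:

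| European share | 24 mo, d = 0 | 24 mo, d = 90 | 18 mo, d = 0 | 18 mo, d = 90 |
|---|---|---|---|---|
| 50% | 119 | 0 | 105 | 0 |
| 60% | 259 | 136 | 245 | 81 |
| 70% | 359 | 236 | 345 | 181 |

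**Effect on precision.** The confidence interval widens by 1/√(1 − lost/1000) − 1.

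| Lost of 1,000 | Basis | Widening |
|---|---|---|
| 160 / 300 / 400 | A, no window allowance | 9.1% / 19.5% / 29.1% |
| 120 / 240 / 340 | B, r = 0.5 | 6.6% / 14.7% / 23.1% |
| 80 / 180 / 280 | Europeans beyond 420th only | 4.3% / 10.4% / 17.9% |
| 0 / 136 / 236 | A, 24 months, d = 90 | 0% / 7.6% / 14.4% |

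These counts are of enrolled subjects. Deaths and withdrawals over 5 years would reduce the number of visits at stake, but the percentage widening is unchanged if that attrition is proportional.

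**The case against.** The strongest reply is that this is a drafting slip. The sentence speaks of both studies and uses a plural for what is a single PMCF population, so its author may have meant both populations. The rule also sets only an earliest time. Waiting for all of Phase II complies with it, and is the only way to deliver SAP 1.4 and 3.1 in full. An early run would postpone the later subjects' data without destroying them, because follow-up continues to 5 years regardless.

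The size is also open to challenge. The only European figure in the documents is a floor of 420, and at that share the overlap under uniform accrual is 0. Shares of 60% or 70% have no support in the text. Europe was the last region approved, which points to a later 420th subject. The accrual time is blacked out in the public protocol.

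Much of this stands as a limit on size: the number affected is unknown and may be 0, and any shortfall could be made good by a later analysis. It does not remove the defect. Where the SAP means both populations it names both (sections 3.2, 3.3 and 3.6); in 2.6 it does not. A slip in the only visible timing rule still needs correcting. Permission to wait is also not a requirement to wait, and nothing in the plan calls for the analysis to be repeated once Phase II is complete.

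**Conclusion.** The concern holds. As written, the EXPAND G4 5-year analysis may be run before all Phase II subjects have reached, left or passed their 5-year visit, because 580 of the 1,000 are outside the condition.

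The textual point depends on no assumption. The size does: from 0 subjects, if the 420th European enrols at the end of Phase II, to 400 under uniform parallel accrual with a 70% European share, with visit windows absorbing part of that and, at a 50% share, possibly all of it. The corresponding widening of visit-based 5-year confidence intervals runs from 0 to about 29%.

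The APS test and its power are unaffected, and the 30-day safety and performance results would be complete well before this analysis. The harm is confined to long-term descriptive results. It should be fixed, but it does not threaten the study's main conclusion.

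**What to change.** Split the second sentence of SAP 2.6 into two triggers:

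- **EXPAND G4:** run the 5-year analysis once every Phase II subject in the primary analysis population has had the 5-year visit, been discontinued, or gone past the end of the 5-year window.
- **PMCF study:** keep the present 5-year trigger, applied to the PMCF population only.

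The cost is one SAP sentence. Design, sample size and data collection do not change. The EXPAND G4 5-year report may come later than under the current rule, but SAP 2.5 already allows descriptive interim reports for regulatory or reimbursement needs, so earlier results can still be issued and labelled as interim.
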